#### **IV. RESEARCH STUDY DESIGN**

---

**Overview and Design of the Proposed Study.** Consistent with our preliminary study, we will recruit (from the Denver and Boulder areas): 450 participants who report a desire to use marijuana to cope with their anxiety, have had previous experience with marijuana, and report a Generalized Anxiety Disorder-7 (GAD-7) score of  $\geq 5$  (at least mild to moderate anxiety) and 75 non-using cannabis controls (matched for anxiety via GAD-7  $\geq 5$ ) who do not report an intention to use marijuana to cope with their anxiety nor any marijuana use over the prior six months. A summary of the Assessment schedule and the additional inclusion/exclusion criteria are detailed below in Table 1 and Section VI (respectively).

All participants will come to the CUChange Lab for a Baseline Appointment (Session 1) involving extensive measures of anxiety (e.g., Depression, anxiety, and stress scale, a rumination induction task, a dot probe task, rumination self-report scale, etc.) and other psychiatric symptoms, health behavior (e.g., stress, quality of life, sleep, alcohol use), the cognitive testing battery utilized in our preliminary studies, a blood draw for biomarkers of inflammation, and a motor battery (**Baseline Appointment, Session 1**). During this Baseline Appointment, a research assistant will provide information on three at-home aspects of the study: 1) the range of assigned cannabis products (e.g., differing THC to CBD ratios possible) and potential prices, 2) the ActiGraph wearable watch device that participants will be loaned to measure physical activity and sleep (during the final 2 weeks of the four week study), and 3) a microbiome collection kit that they will be given to complete (once before and once after 4 weeks of *ad libitum* use of their cannabis product). The experimental aspect of this study will be the assigned cannabis ratio, while the other aspects of this study are *ad libitum* based, with regard to the dosing schedule and choice of product type (flower or edible), by participants that would already like to use cannabis to cope with their anxiety.

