**Marijuana Administration at Home.** Unlike other studies done in the United States to date, the proposed work will utilize a design that allows participants to choose their type of administration and *ad libitum* dosing schedule, but contains an experimental element (i.e., strain assignment). Specifically, at the end of the baseline session, participants will be given instructions to purchase assigned strain, differing by THC to CBD ratio (n=75/flower strain; n=50/edible strain): 1) a THC-based strain akin to a typically used strain with normal levels of THC and little to no CBD (+THC/-CBD), 2) a 1:1 strain with equivalent THC and CBD levels (+THC/+CBD), or 3) a CBD-enriched strain with little to no THC (-THC/+CBD) at a good clinical practice dispensary in Boulder or Denver, Colorado.

The market for flower versus edible cannabis products are similar, but differ slightly in their servings, typical doses, and labeling system (potency listed by percent with flower products rather than by mg with edibles) making it currently impossible to assign identical flower and

edible potency groups, or ratios. However, Colorado requires all strains to be tested by a state licensed lab, which allows us to have a precise measure of potency to operationalize our strain assignments. Therefore, the flower groups will be assigned either the +THC/-CBD strain (containing 18% THC and <1% CBD), a combination of THC and CBD strain (a 1:1 ratio +THC/+CBD containing 12% THC and 12% CBD), or the -THC/+CBD strain (containing <1% THC and 18% CBD). Like the flower group, the edible groups will be assigned to one of the same ratios (an all THC strain, a combination of THC to CBD strain with a 1:1 ratio, or an all CBD strain) and they will choose when and how much they would like to use this assigned edible over the next four weeks. However, the participants that choose to be in the edible group (rather than the flower group), will be assigned an edible product with 10 mg of THC, CBD, or a combination of THC and CBD per edible piece (comparable to the flower products with 6, 12, or 18% THC, CBD, or a combination of THC and CBD).

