an all THC, all CBD, and a combination of THC to CBD group [(+THC/-CBD, +THC/+CBD, and -THC/+CBD, ratios: 1:0, 1:1, and 0:1)].

[figure not shown]
[figure not shown]
To be conservative, we thus estimated an ICC of .50. Using a mixed model ANOVA design, with four groups, three assessment points, and an average ICC = .5 between assessment points, a total  $n=450$  (75 per flower group and the control, and 50 per edible group) will allow us to detect a groupXtime interaction effect as small as  $f=.09$ . In **Aim 2B**, the test of the effects of group on stress-reactivity will again involve four groups ( 3 cannabis and 1 control) but only one assessment point.. Note that our power analysis is conservative, as our actual analysis will involve more powerful tests (e.g., focused interaction contrasts as opposed to overall  $F$  tests). For **Aim 3**, the estimation of the mediational model via path analysis (Hypothesis 3; see Figures 3a and 3b below), Monte Carlo simulation strategies formed the basis of our power analysis. Given that the model in Figure 3b is the more complex of the two, we utilized the model structure with the three planned contrasts as exogenous variables in our simulations. The key test of Hypothesis 3 will involve the use of structural equation modeling techniques. Because we have almost no empirical data on which to base estimates of effect size, we conservatively utilized small to moderate effect sizes depending upon hypothesized relationships. For example, we expect small coefficients (.20) from each contrast to stress reactivity, whereas we expect a slightly larger path (.40) between the contrast comparing the -THC/+CBD strain to control and inflammation. Power analyses were conducted in Mplus and then in SAS following procedures for estimating the power of the likelihood ratio test of the significance of parameters in structural equation models. We utilized Monte Carlo simulation to generate a population covariance matrix based on the hypothesized parameters in the model. For the smallest path in the model (which requires the most power to test), assuming two-tailed alpha of .05, our estimates of power at various sample sizes appear in Table 3. To assure .80 power or better to detect small associations between all groups, we thus require data from 450 participants (75 in the control and each flower group as well as 50 in each edible group) for our mediational analyses.

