*The impact of attrition.* It is anticipated that some attrition will occur. Based on our current pilot study and previous marijuana studies, we anticipate a 10-15% attrition rate between the baseline session and the final four-week follow up session, though we have not experienced and do not anticipate differential attrition by condition. Thus, to allow for attrition, we assume an approximate 85% retention rate over the course of data collection. To adjust for this attrition rate in all groups, we will recruit  $n\approx520$  participants ( $n=86$ /flower or control group as well as 58/edible group). Our approach to power analysis and accounting for attrition is also quite conservative, in that the techniques we will utilize in data analysis use state of the art recommendations for the handling of missing data in longitudinal studies.

**Statistical Analysis Plan.** Analyses will be conducted primarily on the SAS system for Windows Version 9.4 and Mplus Version 7.3, which include capabilities to test multilevel models that appropriately model both normally and non-normally distributed data as well as missing data. To test the success of random assignment across the marijuana strain groups the equivalence of the three marijuana user and control groups across all pretest measures will be assessed via  $t$ -tests on continuous items (e.g., BAI) and  $\chi^2$  tests of categorical items (e.g., race). The Bonferroni approach will be used to correct for alpha inflation (familywise alpha of .05). The distributional properties of continuous variables will be examined to determine appropriate analytic techniques or normalizing transformations prior any analyses.

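### The design overview and the attrition paragraph split recruitment differently between users and controls, and the overview's 75 controls carry no allowance for dropout

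*Combined protocol and SAP*

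**What the plan says.** All the figures are in Section IV of the combined protocol and SAP.

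- **Overview and Design of the Proposed Study** recruits "450 participants who report a desire to use marijuana to cope with their anxiety" and, separately, "75 non-using cannabis controls".
- **Marijuana Administration at Home** gives group sizes at the point of strain assignment: "participants will be given instructions to purchase assigned strain, differing by THC to CBD ratio (n=75/flower strain; n=50/edible strain". It does not say whether these are numbers recruited or numbers needed for analysis.
- **Power Analysis and Sample Size Requirements** states the number needed for the mediation model: "we thus require data from 450 participants (75 in the control and each flower group as well as 50 in each edible group". Here 450 is the total with data, controls included. The group x time calculation uses the same total and the same breakdown.
- **The impact of attrition** says "we anticipate a 10-15% attrition rate between the baseline session and the final four-week follow up session" and "we assume an approximate 85% retention rate over the course of data collection". It continues: "To adjust for this attrition rate in all groups", the study will recruit about 520, with 86 per "flower or control group as well as 58/edible group".

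**The concern.** The overview and the attrition paragraph both state how many people the study will recruit, yet they differ by 18 users and 11 controls. The power section shows what 450 stands for: everyone with data, controls included. The overview gives that same number to users alone and adds 75 controls, which is exactly the number of controls required with data. One possible explanation, which the documents do not confirm, is that the overview took the analysis total for the number of users.

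If recruitment followed the overview, any shortfall would fall wholly on the non-users. They are recruited under their own eligibility criteria (Section VI), so surplus users cannot replace them. They are a comparator in Hypotheses 1, 2A and 2B. They form one side of the only predictor in mediation Model 3a. They are also the reference for the larger (.40) path to inflammation assumed in the power section.

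**Working it through.** **Inputs.** Required with data: 75 controls, 75 per flower group, 50 per edible group (power section). Recruited: 450 users and 75 controls (overview), or 86 per flower or control group and 58 per edible group (attrition paragraph). Attrition 10-15%, retention about 85% (attrition paragraph).

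**1. The plan's own totals.**
- Required with data: 4 x 75 + 3 x 50 = 450, of whom 3 x (75 + 50) = 375 are users and 75 controls.
- Attrition paragraph: 4 x 86 + 3 x 58 = 518, which agrees with the stated figure of about 520. Users: 3 x (86 + 58) = 432; controls: 86.
- Overview: 450 + 75 = 525.

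**2. Attrition allowance implied by each split** (1 - required/recruited).
- Overview: users 1 - 375/450 = 16.7%; controls 1 - 75/75 = 0%.
- Attrition paragraph: flower and control groups 1 - 75/86 = 12.8%; edible groups 1 - 50/58 = 13.8%; overall 1 - 450/518 = 13.1%.

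**3. Numbers left under the overview.**
- Controls: 75 x 0.85 = 63.75 and 75 x 0.90 = 67.5, so about 64-68 against 75.
- Users: 450 x 0.85 = 382.5 and 450 x 0.90 = 405, so about 383-405 against 375.

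**4. Effect on precision under the overview.** The relative standard error of a difference is sqrt(1/a + 1/b), where a and b are the numbers retained. This assumes equal variances, users spread evenly over the three ratios, and completers only.

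| Contrast | As planned | 15% attrition | 10% attrition |
|---|---|---|---|
| All users v controls | 375/75: .1265 | 382.5/63.75: .1353 (+6.9%) | 405/67.5: .1315 (+3.9%) |
| One ratio group v controls | 125/75: .1461 | 127.5/63.75: .1534 (+5.0%) | 135/67.5: .1491 (+2.1%) |
| One ratio group v another | 125/125: .1265 | 127.5/127.5: .1252 (-1.0%) | 135/135: .1217 (-3.8%) |

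**5. Overall group x time test.** Inputs are the plan's f = .09, ICC = .5, four groups, three times and alpha .05. Noncentrality = f^2 x N x 3/(1 - .5), with 6 and 2(N - 4) degrees of freedom. Power is .958 at N = 450, .957 at N = 446 (525 x 0.85) and .954 at N = 440 (518 x 0.85).

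**6. Where 86/58 comes from.** Multiplying by 1.15 gives 75 x 1.15 = 86.25, 50 x 1.15 = 57.5 and 450 x 1.15 = 517.5, which fit the stated figures. Dividing by 0.85 gives 88.2, 58.8 and 529.4. The documents do not show the derivation, so multiplication is an inference. At exactly 85% retention, 86 x 0.85 = 73.1, 58 x 0.85 = 49.3 and 518 x 0.85 = 440.3, against 75, 50 and 450. The retention that meets the requirement is 75/86 = 87.2%, 50/58 = 86.2% and 450/518 = 86.9%. On the contrasts in step 4, the standard errors at 85% retention rise by only 1.1% to 1.3%.

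**The case against.** The best defence is that the overview is only a summary. It ends by pointing forward to later text on the sample and the power analysis. The attrition paragraph gives the worked, per-group figures, and the two totals (525 and about 520) differ by roughly 1%. A reader therefore has good reason to prefer the attrition paragraph. That stands as a reason for choosing its figures in the correction. It does not remove the conflict: no text gives either statement precedence, and the matching totals conceal a different split.

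It is also fair to say that step 4 gives an upper bound. The plan intends missing-data methods and random coefficient models, which can use earlier sessions from people who leave, so the real loss of precision should be smaller.

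Three stronger inferences are tempting and are not supported.

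- **That 375 users is a third recruitment target.** The 75 and 50 given under Marijuana Administration at Home are never called that, and they equal the power section's numbers with data. They are only unlabelled, at a point where recruited numbers would be expected.
- **That 86/58 contradicts the retention assumption.** The plan says approximately 85% and expects 10-15% attrition. The allowance implied by 86/58 lies inside that range, and the shortfall at exactly 85% is about 10 in 450.
- **That the trial is underpowered.** The overall group x time power hardly moves and stays well above the planned .80.

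**Conclusion.** The recruitment split is inconsistent as written: 450 users and 75 controls in the overview, 432 users and 86 controls in the attrition paragraph. The overview's control figure is the number required with data and has no attrition allowance, although the attrition paragraph applies its adjustment to every group.

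If the overview was followed, and if the plan's attrition range applies equally to users and controls, the control group ends about 7 to 11 short of 75. The cost is a modest loss of precision in the comparisons with non-users, bounded by the completers-only figures above. The contrasts between strains, which the overview places at the centre of the primary hypotheses, are not weakened. The effect on mediation power cannot be checked, because Table 3 is not in the text available here. The 86/58 arithmetic is a minor note. The point merits correction because it concerns the sample size itself and costs almost nothing to put right.

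**What to change.** 1. In the overview, replace 450 users and 75 controls with 432 users and 86 controls, 518 in all.
2. Under Marijuana Administration at Home and in the power section, label 75 and 50 per group as numbers required with data.
3. In the attrition paragraph, either state that 86/58 assumes about 87% retention, or keep 85% and state that about 440 are expected with data (73 per flower or control group, 49 per edible group).
4. If enrolment has closed, report the numbers actually enrolled and the numbers with Session 3 data, by ratio, product form and control group. The Spring 2023 amendment suggests that it may have closed, since it contacts people who have already finished. A revised target alone would then be retrospective; the actual counts show whether the control group reached 75.

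**Cost.** Text only, if recruitment followed the attrition paragraph. If it followed the overview and is still open, the change means 11 more controls and 18 fewer users, within a total 7 smaller than the overview's own 525.

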Because the long-term goal of this work is to better understand the effect of different levels of cannabinoids in anxiety patients, as they are used real world, we decided that it was critically important to emphasize external validity in both the flower and edible forms of cannabis use. The disadvantage of our design is that we have little control over how the participants use the marijuana or how much they use. To address this limitation, both in our pilot study and in this application, we rely on blood quantitation of cannabinoids (from both flower and edible users) to determine the level of THC and CBD in each subject. Thus, regardless of how the participant uses the marijuana, we have an objective measure of the dose received for both THC and CBD for each subject, which is the sine qua non of pharmacological research. This aspect is also critical for our analytic approach, which allows for the analysis of THC and CBD blood levels as continuous measures. In this way, we also capitalize on the greater variability in blood levels expected in the design by analyzing overall levels of CBD and THC as well as by strain, which by design (in flower and edible forms) will have different THC/CBD ratios. This further allows for a direct test of whether any differences in outcomes for participants randomly assigned to the -THC/+CBD strain are due to an increase in CBD or a decrease in THC as compared to their Baseline. This strain is a critical comparison as there are data to suggest that the effects of THC differ when CBD is also in the blood.

**Power Analysis and Sample Size Requirements.** Sample size was selected to permit analysis of the primary research questions at two-tailed alpha of .05 and power level of .80. Estimates of effect size follow Cohen and were conducted in G\*Power 3. The primary analyses in **Aims 1-3** broadly is the test of the group X time interaction effects across repeated assessments of THC/CBD and anxiety, inflammatory markers, and stress reactivity. For the current data analysis plan, we will only focus on the ratios and time points that we currently have supporting preliminary data for and hypothesize to have the greatest impact on anxiety. Hence, in this data analysis plan we will focus on the 3 main time points (out of 4) for a chronic use endpoint [Baseline, 2 Week, and 4-Week Pre-administration (Sessions 1-3)] and the 3 main cannabis product so that there will be

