**Specific Aim 1** – To compare changes in anxiety in mild to moderately anxious marijuana users exposed to 4 weeks of use of one of three different marijuana strains (+THC/-CBD vs. +THC/+CBD vs. -THC/+CBD) to a group of non-using controls matched on anxiety. *Hypothesis 1* predicts a main effect of strain such that -THC/+CBD marijuana users will have lower levels of anxiety (BAI) compared to other marijuana groups and to non-using controls. To examine the main effects of group on these outcomes, we will estimate a random coefficient regression (RCR) models in SAS Proc Mixed wherein the change in BAI scores will be regressed on marijuana user group, time, and the groupXtime interaction. *Hypothesis 1* also predicts that higher CBD levels in blood among marijuana users will be associated with lower BAI. The analysis for this hypothesis will again be a RCR model, but instead of group membership, the independent variables in these models will be level of CBD in blood, time, and the CBDxtime interaction. We will conduct additional models to explore whether there may also be main effects of THC in blood or a THCXCBD interaction effect on BAI. Secondary models will test the effects of strain and /or cannabinoid blood levels on the daily and monthly assessments of anxiety using a multi-level modeling approach. These additional analyses will appropriately control for Type I error, depending upon the number of tests run. Co-I [name] has used such models extensively in prior work.

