**Specific Aim 2** - To assess inflammation and stress reactivity [biological and behavioral stress change scores during a stress induction (TSST)] in mild to moderately anxious marijuana users exposed to 4 weeks of use of one of three different marijuana strains compared to a group of non-using controls matched on anxiety. *Hypothesis 2A* predicts a main effect of strain such that -THC/+CBD marijuana users will have lower levels of circulating peripheral inflammatory markers compared to other marijuana groups and to non-using controls. To examine the main effects of group on these outcomes, we will estimate a random coefficient regression (RCR) models in SAS Proc Mixed wherein the summary values of the panel of inflammatory markers utilized in our preliminary study will be regressed on marijuana user group, time, and the groupXtime interaction. *Hypothesis 2A* also predicts that higher CBD levels in blood among marijuana users will be associated with lower levels of circulating peripheral inflammatory markers. The analysis for this hypothesis will again be a RCR model, but instead of group membership, the independent variables in these models will be level of CBD in blood, time, and the CBDxtime interaction. We will conduct additional models to explore whether there may also be main effects of THC in blood or a THCXCBD interaction effect on inflammatory markers. *Hypothesis 2B* predicts a main effect of strain on reduced stress reactivity. RCR models in SAS will again be utilized, wherein stress reactivity (pre-rumination induction–post rumination induction change scores of self-report, state anxiety, and inflammatory markers) will be regressed on marijuana user group. *Hypothesis 2B* also predicts that higher CBD levels in blood among marijuana users will be associated with even lower stress reactivity. As in the test of *Hypothesis 2A*, we use RCR wherein the independent variables in these models will be level of CBD in blood. As with Aim 1, we will conduct additional models to explore whether there may also be main effects of THC in blood or a THCXCBD interaction effect on stress reactivity, with appropriate Type 1 error corrections.

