**Specific Aim 3** - To test indirect effects of marijuana use on anxiety (BAI) via inflammatory markers and stress reactivity in anxious marijuana users exposed to 4 weeks of use of one of three different marijuana strains compared to a group of non-using controls matched on anxiety. Hypothesis 3 will test mediational models that ask whether the effect of marijuana use and strain on anxiety is mediated by changes in inflammation, stress reactivity, or both. To this end, we will estimate the mediational models in Figures 3a and 3b via structural equation modeling. To test the overall effect of use of marijuana versus non use, we will estimate model 3a wherein the sole exogenous variable is marijuana users (coded as 1) versus non-users (coded as 0). The mediators will be change in inflammation from Session 1 to Session 3 and stress reactivity at Session 3. The outcome variable is change in anxiety from Session 1 to Session 3. This model will be estimated and both the fit of the model and the significance of the path coefficients will be examined. Importantly, we will compare the path coefficients from user status to inflammation versus stress reactivity to determine whether use is associated with changes in inflammation, stress reactivity, or both. Assuming that the paths from inflammation and stress reactivity to anxiety are significant, we can test whether there are indirect effects of user status on anxiety that are mediated by inflammation, stress reactivity, or both. A test for completeness of mediation is employed through a 1 degree of freedom  $\chi^2$  test where a path directly from user status to anxiety is added to the model. A nonsignificant direct path and a nonsignificant change in  $\chi^2$  suggest that user group effects on the anxiety were mediated through the theoretical mediational constructs. A secondary test of mediation will utilize bootstrap methods to test the significance of, and confidence limits around, the mediated effect. Similar mediational analyses have been widely used by Co-I [name]. The model depicted in Figure 3b will test the more focused hypothesis that the ratio of cannabinoids is critical for the biological and behavioral changes that drive anxiety. The analysis will follow identical procedures to those described to test Model 3a. Finally, it is also possible to use continuous values of THC and CBD in blood as the exogenous predictors in the model.

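### Hypothesis 2A is sized on group × time but tested by a group main effect on marker level, which takes in the pre-product draw and any standing gap from non-users; Hypothesis 1 leaves its deciding term open

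*Combined protocol and SAP*

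**What the plan says.** Section IV, Power Analysis and Sample Size Requirements, says the primary analysis in Aims 1 to 3 "broadly is the test of the group X time interaction effects across repeated assessments", and limits the plan to Sessions 1 to 3. It states that N=450 "will allow us to detect a groupXtime interaction effect as small as" f=.09, and that the actual tests will be more powerful, for example "focused interaction contrasts as opposed to overall" F tests.

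Section IV, Statistical Analysis Plan, then words both hypotheses differently.

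- **Hypothesis 2A** (Specific Aim 2) "predicts a main effect of strain such that -THC/+CBD marijuana users will have lower levels of circulating peripheral inflammatory markers" than the other groups. The model, fitted to examine the main effects of group, is one "wherein the summary values of the panel of inflammatory markers utilized in our preliminary study will be regressed on marijuana user group, time" and their interaction. The outcome is the marker level.
- **Hypothesis 1** (Specific Aim 1) "predicts a main effect of strain such that -THC/+CBD marijuana users will have lower levels of anxiety (BAI"), but the model is one "wherein the change in BAI scores will be regressed on marijuana user group, time, and the groupXtime interaction". The hypothesis is on level and the outcome is change.

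No interaction contrasts are listed for either hypothesis, and neither model states how time is coded. For change in BAI, Aim 1 does not say from which session or at which sessions. Aim 3 does: "The outcome variable is change in anxiety from Session 1 to Session 3".

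**The concern.** For 2A the two sections name different deciding terms. A group main effect on level over Sessions 1 to 3 uses the Session 1 draw, which precedes purchase of the assigned product (Section IV, Marijuana Administration at Home; Section XII, Baseline Appointment). It also carries in any difference that was there at the start.

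Among the randomised strains such a difference is chance. Against the non-users it need not be. They are not randomised, are matched only through a GAD-7 score of at least 5, and have not used cannabis for six months. The plan's own background holds that cannabinoids lower inflammation, so a standing marker gap is plausible. The planned baseline equivalence tests include the controls, but nothing in the Aim 2 model uses their result. A gap that existed before the study could therefore be reported as a product effect.

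For Hypothesis 1 the risk is smaller. The model has two candidate terms, they answer different questions, and the plan does not choose between them.

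**Working it through.** **Inputs from the plan:** 75 per flower group and control, 50 per edible group, so 75+50=125 per strain and 3×125+75=450; four groups; three assessments; correlation 0.5; two-sided 0.05; power 0.80.

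**Assumptions (the documents give no SD, effect profile or gap):** SD 1; equal correlation ρ between sessions; a strain effect of 0.35 SD at Session 3 that is full, half or absent at Session 2; a stable control gap of 0.1, 0.2 or 0.3 SD.

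**Step 1. The plan's own figure.** Interaction: λ = f²·450·3/(1−ρ) = 0.0081×1350/0.5 = 21.87, with 6 and 892 df. Power at f=.09 is 96%, and the smallest f at 80% is .071. A sphericity factor of 0.5, which the plan does not state, gives .090. The figure is therefore not called wrong here.

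**Step 2. Each test as a contrast.** With weights w on Sessions 1, 2 and 3, variance = ρ(Σw)² + (1−ρ)Σw². SE = √[variance×(1/n₁+1/n₂)]. A stable gap g shifts the contrast by g·Σw. At ρ=0.5:

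| Test | Weights | Variance | Σw |
|---|---|---|---|
| Group effect on level, categorical time | 1/3, 1/3, 1/3 | 0.667 | 1 |
| Group term, numeric time centred at Session 1 | 5/6, 1/3, −1/6 | 0.917 | 1 |
| Group term, numeric time centred at Session 3 | −1/6, 1/3, 5/6 | 0.917 | 1 |
| Session 3 minus Session 1 | −1, 0, 1 | 1.0 | 0 |
| Session 3 adjusted for Session 1 | −ρ, 0, 1 | 0.75 | 0.5 |

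Every version of the level term has Σw=1, so the whole gap enters whatever the time coding.

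**Step 3. One strain v controls, 125 v 75, no product effect.** For a 0.2 SD gap with categorical time, SE = √(0.667×0.02133) = 0.119 and 0.2/0.119 = 1.68, which is significant 39% of the time. For gaps of 0.1/0.2/0.3 SD:

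- level, categorical time: 13/39/71%
- level, numeric time centred at Session 1 or 3: 11/30/57%
- Session 3 adjusted for Session 1: 7/12/22%
- change from Session 1: 5%

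For a 0.2 SD gap at ρ=0.3 and 0.7, the categorical level term gives 46% and 33%, and the adjusted contrast 17% and 9%.

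**Step 4. Two strains, 125 v 125, effect full/half/absent at Session 2.** For example, with a full effect and categorical time, 0.35×2/3 = 0.233, SE = √(0.667×0.016) = 0.103, ratio 2.26, power 61%.

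| Test for 2A | Full | Half | Absent |
|---|---|---|---|
| Level, categorical time | 61% | 39% | 20% |
| Level, numeric, centred at Session 3 | 92% | 82% | 67% |
| Level, numeric, centred at Session 1 | 8% | 5% | 8% |
| Group × time, categorical (2 df) | 82% | 69% | 82% |
| Group × time, numeric slope | 79% | 79% | 79% |
| Session 1 to 3 change | 79% | 79% | 79% |
| Session 3 adjusted for Session 1 | 89% | 89% | 89% |

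Over ρ from 0.3 to 0.7, the categorical level term has 71–54%, 47–34% and 24–18%, and the adjusted contrast 82–97%.

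**Step 5. Four-group tests, categorical time.** For one profile p, main-effect f / interaction f = mean(p)/SD(p), so interaction f=.09 implies main-effect f of .127/.110/.064. For the main effect λ = f²·1350/(1+2ρ), with 3 and 446 df. At f=.09 the interaction has 96% power and the 2A main effect 80/66/25%. With the interaction at 80%, the main effect has 58/45/17%. The loss is not universal: at ρ=0.3 a full early effect gives the main effect 84% when the interaction has 80%.

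**Step 6. Hypothesis 1.** If change from Session 1 is entered at Sessions 2 and 3, the group main effect is the mean of Sessions 2 and 3 minus Session 1 (weights −1, ½, ½; variance 0.75). Those weights sum to zero, so it is a group × time contrast on level. Power is 89/67/36%. Group × time inside that model is Session 3 minus Session 2 (variance 1.0), with power 5/28/79%.

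**The case against.** The strongest reply is that the 2A wording is loose and nothing more. The Aim 2 model contains group × time, the power section names that term as primary for all three aims, and Aim 3 treats inflammation as change from Session 1 to Session 3. If the power section governs, a stable gap does no harm. That is true, but Aim 2 states the hypothesis as a main effect and fits the model to examine it, and no text says the power section prevails.

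Other objections limit the point:

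- A reader might infer that Hypothesis 1 is contradictory in the same way. The documents do not support that. Aim 1 sets out to compare changes, a group effect on change from Session 1 is one of the focused interaction contrasts the power section announces, and the main effect is the more natural reading of Aim 1.
- A reader might infer that testing a main effect for 2A always costs power among the strains. It does not. Random coefficient regression would ordinarily use numeric time, and centred at Session 3 the group term does better than the interaction if the effect is full or half present by week 2 (92% and 82% against 79%).
- The control gaps of 0.1 to 0.3 SD have no source in the documents. They show sensitivity and do not predict a gap.
- Requiring the Session 1 covariate goes beyond removing the contradiction. A change contrast removes it too, and the covariate is there for precision.

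**Conclusion.** For Hypothesis 2A the contradiction is real and should be fixed. Followed as written, Aim 2 tests a term that was not sized and that passes a standing user/non-user gap through in full under any time coding. At an assumed 0.2 SD gap it is significant in 30% to 39% of studies with no product effect (ρ=0.5), against 5% for change from Session 1. That result rests on the gap being stable and on equal correlation between sessions. The effect on power among the strains has no single size: it runs from 5% to 92% across the codings and profiles tried.

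For Hypothesis 1 the defect is an unnamed deciding term and time coding, with a mismatch between a hypothesis on level and an outcome of change. It would do serious harm only if group × time inside the change model were taken as deciding, when an effect complete by week 2 would be detected 5% of the time.

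**What to change.** Reconcile Specific Aim 2 with the power section by dropping the group main effect on levels that include Session 1. Then, for both hypotheses:

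1. Model the Session 2 and Session 3 values on group, categorical time and group × time, with the Session 1 value always a covariate. At present Table 2 mentions adjusting for baseline BAI only if necessary.
2. Among the three randomised strains, name the Session 3 contrast as deciding. A fixed order of contrasts is optional.
3. Against non-users, name the difference in Session 1 to Session 3 change as deciding. State that it assumes the gap would stay stable without the product. Report the baseline-adjusted estimate as supportive, because at ρ=0.5 adjustment leaves half of a standing gap in place (Σw=0.5).
4. Restate power for the contrasts chosen.

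A simpler alternative is acceptable: the Session 1 to Session 3 change contrast throughout, at 79% instead of 89% power among strains (0.35 SD, ρ=0.5).

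The cost is wording only, since the Session 1 to 3 values are already scheduled. The control comparison becomes less precise: the difference detectable with 80% power is 0.41 SD by change against 0.36 SD with baseline adjustment at ρ=0.5 (0.49 v 0.39 at ρ=0.3, 0.32 v 0.29 at ρ=0.7).
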